Methodology:	
Research design. The RTM Protocol effectiveness study implies a randomised field trial comparing RTM with treatment-as-usual (TF-CBT, EMDR or pharmacotherapy). It is chosen and will be standardised based on CONSORT 2010 Statement: reporting parallel group randomised trials. To enhance the external validity of the findings, all the interventions are planned to be explored among three different settings of mental health care accustomed to Ukraine: mental health hospital care (inpatient and outpatient care for veterans) and psychotherapeutic practice (for civil trauma survivors).
 
Measures. Primary outcome effectiveness measures are MH professional proved existence or loss of PTSD diagnosis and/or PTSD symptoms severity measured by PTSD Checklist PCL-5 (re-experiencing of trauma, avoidance of trauma-related stimulus, negative alterations in cognition and mood, hyper-arousal).
 
Among secondary outcome measures will be the existence and severity of depression and anxiety-related symptoms according to PHQ-9 and GAD-7 scales.
 
Data analysis. Descriptive Statistics: means, SDs, medians, frequencies and percentages, baseline comparability between groups (t-tests, chi-square tests). Primary and Secondary Outcome Analysis: mixed-effects repeated measures ANOVA. Handling Missing Data: multiple imputation or maximum likelihood estimation under MAR assumption. Effect Size Reporting: Cohen's d, odds ratios, and 95% confidence intervals.
 
Data collection will be in Ukrainian language (all the scales are validated in Ukrainian and recommended by the World Health Organisation for the screening of the mentioned mental health conditions) at baseline (diagnostic session), 1 month after complete treatment application, in 6 months (follow-up booster session), and in 12 months (second follow-up booster session).

Study 2: The RTM Protocol and Training Feasibility Study

Target sample size: (Please justify the target sample size, either statistically or by referring to existing literature)	
The research sample for the FEASIBILITY STUDY is expected to be 20 participants according to the trauma-related cases/workforce availability ratio of implementing partners: 10 persons from each site.
 
The number of clients is expected to be 60 persons (persons treated with the RTM Protocol) according to the RTM Protocol effectiveness study description.

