Key inclusion criteria:	
Key inclusion criteria for MH professionals are (1) holding an accomplished higher education degree in the mental health area (psychology, psychiatry, psychiatric nursing, clinical social work), (2) having at least three years of hands-on clinical experience in mental-health settings, (3) being formally trained to deliver mental health care

	
to people exposed to trauma through accredited coursework, supervised practice, or equivalent, (4) meeting Ukrainian licensing and registration requirements mandated by health-care regulations and the implementing organisation's internal policies, (5) committing to attend the full training, complete all associated supervision sessions, and deliver the Protocol as specified by the study timeline.
 
The client sample is the same as for the study 1.

Key exclusion criteria:	
Key exclusion criteria for MH professionals are (1) being under investigation, suspension, or other disciplinary action by a professional body or employer, (2) lacking mandatory professional continuing education for the last year (min 40 hours), (3) having caseload exceeding the threshold for service quality requirements (> 30 active therapy clients).
 
The client sample is the same as for the study 1.

Age range of participants:	
Adults aged 18-65 (with regard to the eligibility criteria).
 
The same sample as for the study 1.

Country/ies of recruitment:	
Ukraine

Expected duration of procedure:	
MH Professional will be engaged into case statistic collection (30 min per case, 1 hour per person); satisfaction surveying (15 min per person) and focus-group interviews (1,5 hour of group work).
 
Clients will be engaged into satisfaction surveying (15 min per person).

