Data Collection:	
Intervention Usability Scale, satisfaction survey; audio-recorded focus-groups interviews.
 
Data on MH professionals' occupation, place of work, professional experience, trauma-centred methods used; data from Intervention Usability Scale and case statistics (number of trauma-related requests, trauma-specific cases treated with the RTM, hours spent for each case treatment, process comfort, expected and reached results, usefulness for different types of trauma and trauma-related symptoms), will be collected from printed questionnaire sheets filled in by participants.
 
Data on MH professionals' Protocol use features, implementation benefits and challenges, effects and consequences, clients' acceptance and perception will be collected and audio-recorded during focus-group interviews.
 
MH professionals' names, email-address, phone number will be collected from printed informed consent.
 
Data on clients' treatment satisfaction (process comfort, expected and reached results, usefulness for client's types of trauma and trauma-related symptoms) will be collected from printed questionnaire sheets filled in by participants.

	
Clients' names, email-address, phone number will be collected from printed informed consent.
 
Data transfer. Aggregated, fully anonymised raw data will be shared by implementing partners' coordinators through Zenodo under closed access and using the EUSurvey Platform (an online survey-management system developed by the European Commission) only with PI [name].

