Methodology:	
Research design. The RTM Protocol and Training feasibility study will evaluate the RTM Protocol acceptability and adaptability during training and practice through case statistics, satisfaction surveying of MH practitioners and clients, and focus-group interviews with MH practitioners. As a standardisation base for the feasibility study the Framework for the development and evaluation of complex interventions issued by the National Institute for Health and Care Research (NIHR) was chosen.
 
Measures. To assess the RTM Protocol's acceptability by MH professionals, case statistics such as the number of trauma-related requests, trauma-specific cases treated with the RTM, hours spent for each case treatment, etc., will be collected. The standardised Intervention Usability Scale will also be applied.
 
Also, satisfaction with the procedure and therapeutic process from both sides (clients and MH professionals) will be surveyed regarding process comfort, expected and reached results, usefulness for different types of trauma and trauma-related symptoms, etc.
 
MH professionals' feedback will also be considered during the focus-group analysis. The focus-group protocol and script will be developed with input from every implementing partner to match the local frame of mental health care. The script previews topics such as the RTM Protocol use features, the RTM Protocol implementation benefits and challenges, the RTM Protocol effects and consequences, the RTM Protocol clients' acceptance and perception, etc.
 
The RTM Protocol's adaptability will be measured by analysing the case statistics and MH professionals' feedback for the Ukrainian version of the protocol.
 
Data analysis. For Quantitative Analysis will be utilised descriptive statistics (frequencies, means, SDs for usability and satisfaction scores), correlation analysis (between usability scores and satisfaction or case outcomes (e.g., Spearman's rho)).
 
Qualitative Analysis will be conducted using thematic analysis (transcripts coded using inductive and deductive approaches, themes mapped to NIHR framework domains), charting and mapping.

SECTION 5: RISK ASSESSMENT AND RISK MINIMIZATION

Study 1: The RTM Protocol Effectiveness Study

Potential risk(s)	Extent of risk(s) and measures taken

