
Human participants are involved in the study with potential risk related to
 
 Physical harm
 
 Psychological harm
 
 Invasion of privacy
 
 Social and economic harm
 
 Other
	
Personal data will be collected (see data collection section).
 
Data collection measures. Implementing partners' coordinators will collect data using printed versions of questionnaires (which will be destroyed after data e-input and prior this time they will be stored in a secure storage cabinet) and focus-group interviews audio-recordings with following transcription. Mental health professionals involved in the research will collect data on clients (people with PTSD) using printed versions questionnaires which will be destroyed after data e-input and before it will be stored in a secure storage cabinet.
 
Data Storage measures. The e-data will be stored on encrypted hard drives and will be accessible only to implementing partners' coordinators. They will create password-protected access to the data with the help of the organisations' IT departments.
 
Data Pseudonymization measures. The data will be anonymized by the implementing partners' coordinators.
 
Usage and storage of personal data will fully comply with Ukrainian legislation, the Civil Code of Ukraine, and the Law of Ukraine on the Protection of Personal Data.
 
No mentioned non-anonymized personal data will be used for the research purposes, transferred or processed in Luxembourg.

Are there any specific risks to the human participants involved, if any.
	
There are no anticipated specific risks for the human participants.

SECTION 6: DATA PROTECTION

Study 1: The RTM Protocol Effectiveness Study

The Project PI will have access only to aggregated, anonymised data. The implementing partners' coordinators and professionals involved in the research will collect, pseudonymise (for the purpose of follow-up assessment in two weeks, six months, and one year), and anonymise the clients' data. Implementing partners' coordinators will aggregate the data and input it on the EU Survey Platform (an online survey-management system developed by the European Commission) to transfer it to Luxembourg. The transferred data will be stored on the University of Luxembourg-protected server ATLAS for up to 10 years.

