Data collection. *Implementing partners' coordinators ([name] from the RCFG, [name] from the NPA) will collect data on MH professionals using printed versions of questionnaires and focus-group interviews audio-recordings with the following transcription. All the data will be destroyed after data digital entry (made by coordinators) and prior to this time they will be stored in a secure storage cabinet and on encrypted hard drives.*

Mental health professionals involved in the research will collect data on clients (people with PTSD) using printed versions of questionnaires and clinical scales, which will be destroyed after data digital entry (made by coordinators) and prior to this time they will be stored in a secure storage cabinet.

Data Storage. *The e-data will be stored on encrypted hard drives and will be accessible only to implementing partners' coordinators. They will create password-protected access to the data with the help of the organisations' IT departments.*

Data Pseudonymization. *The implementing partners' coordinators ([name] from the RCFG, [name] from the NPA) will pseudonymize the data for follow-up assessments.*

Data sharing. *Aggregated, fully anonymised raw data will be shared by implementing partners' coordinators ([name] from the RCFG, [name] from the NPA) through Zenodo under closed access and using the EUSurvey Platform (an online survey-management system developed by the European Commission) only with PI [name].*

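### Study 2's acceptability ratings are collected by people with a stake in RTM, with no stated safeguard against courtesy responding

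*Protocol*

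**What the plan says.** The first objective of Study 2 (Section 2) is the acceptability of RTM among professionals and clients. Section 4, Study 2, Methodology bases this partly on ratings: the Intervention Usability Scale for professionals, focus groups, and a survey in which "satisfaction with the procedure and therapeutic process from both sides (clients and MH professionals) will be surveyed". It also uses case statistics, such as the number of cases treated with RTM and the hours per case.

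The collection routes are fixed in the text:

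- **Professionals.** Section 6, Data access, says that the partners' coordinators "will collect data on MH professionals using printed versions of questionnaires and focus-group interviews audio-recordings with the following transcription". The same coordinators do the data entry. The sample is 20, set "according to the trauma-related cases/workforce availability ratio of implementing partners: 10 persons from each site" (Section 4, Study 2, Target sample size).
- **Clients.** Section 5, Study 2, says: "Mental health professionals involved in the research will collect data on clients (people with PTSD) using printed versions questionnaires". Section 6, Data access, repeats this: "Mental health professionals involved in the research will collect data on clients (people with PTSD) using printed versions of questionnaires and clinical scales". The content of the client sheets is given in Section 4, Study 2, Data Collection: "Data on clients' treatment satisfaction (process comfort, expected and reached results, usefulness for client's types of trauma and trauma-related symptoms".
- **Who the professionals are.** Eligibility for Study 2 (Section 4, Key inclusion criteria) requires "committing to attend the full training, complete all associated supervision sessions, and deliver the Protocol as specified by the study timeline".

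**The concern.** A satisfaction or usability rating is only as candid as the respondent feels free to be. Here a client's opinion of the therapy passes through the group of professionals who deliver it. A professional's opinion passes through a coordinator of one of the organisations implementing it. In both cases the easy answer is the favourable one.

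A comparative study might see such a shift in both arms and lose some of it in the difference. Study 2 has no such protection: professionals rate only RTM, and the clients counted for Study 2 are those treated with RTM. Any shift goes straight into the acceptability result, which Section 2 says will inform humanitarian response policy. The point concerns Study 2's ratings and focus groups only, not the Study 1 symptom scales.

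**Working it through.** The point turns on who handles each instrument, so the check is a trace through the Protocol.

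**1. The numbers of raters reproduce.** Professionals: 2 sites × 10 = 20, as stated. Clients: 3 RTM groups × 20 (Section 6, Study 1) = 60, as stated in Section 4, Study 2. Neither group has a comparator for these ratings.

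**2. Route of the client sheet.**
- Filled in by the client on paper (Section 4, Study 2, Data Collection).
- Collected by mental health professionals involved in the research (Section 5, Study 2; Section 6, Data access).
- Study 2 professionals must commit to delivering RTM (Section 4, Key inclusion criteria), so the collecting group includes people whose therapy is being rated.
- Entered by the coordinator, after which the paper is destroyed (Section 6, Data access).

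**3. Route of the professionals' data.**
- Usability and satisfaction sheets and focus-group recordings are collected by the partners' coordinators (Section 5, Study 2; Section 6, Data access).
- Occupation, place of work and professional experience are collected along with the ratings (Section 4, Study 2, Data Collection). In a site group of 10, these can make a respondent recognisable to a coordinator who knows the staff.
- The same coordinators enter, anonymise and aggregate the data (Section 6, Study 2). Before transfer only they have access.

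**4. Do the stated protections help?**
- *Anonymisation* is done by the collectors after collection. It protects what reaches Luxembourg, but not candour when the form is filled in.
- *Self-completion* keeps the collector from filling in the answers, but not from seeing them.
- *Restricted access* leaves the data with the coordinators.
- *Destruction of paper* after entry means that entries cannot later be checked against source.
- Sealed return, an independent collector and an independent focus-group moderator are not mentioned anywhere.

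**5. Effect on the planned analysis.** Section 4, Study 2 plans frequencies, means, SDs and correlations. If each rating is raised by an amount b, the expected mean is the true mean + b, whether n is 20 or 60; a larger sample does not reduce b. A uniform b leaves Spearman's rho unchanged, so the exposure lies in the levels of the ratings (means and frequencies). The Protocol gives no figure from which b could be estimated, so no numerical bias is offered here.

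**The case against.** The best case against the point has five parts.

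- **Stronger readings are not in the text.** A reader might infer that each client hands the sheet to his or her own therapist. The Protocol says only that professionals involved in the research collect it, and for follow-up paperwork in Study 1 it lists assessors and other professionals besides therapists (Section 6, Study 1). A reader might also infer that each coordinator handles only the staff of his or her own organisation, or moderates the focus group. The coordinators are named together without a pairing, and no moderator is named. These inferences are plausible, but they are not established.
- **Direction and size are not shown.** This is right. An upward shift is what one would expect of courtesy responding, but nothing in the Protocol demonstrates or quantifies it.
- **Acceptability does not rest on ratings alone.** Also right. Case statistics are counts and hours, which courtesy affects less, and they contribute to the same objective.
- **How sheets are returned is site-procedure detail.** This stands only in part. The manner of handover is indeed open, but who collects is a stated rule, and following it as written exposes the answers.
- **The limitations are acknowledged.** Section 6 describes the samples as small and purposive and promises disclaimers on scope and limitations. That wording concerns generalisation and misuse of the data; it does not address candour of response.

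What remains is that interested parties collect the ratings and the Protocol states no shield.

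**Conclusion.** The point holds in a limited form. As written, Study 2's satisfaction and usability ratings and focus-group data pass through people with an interest in RTM, without a stated safeguard and without a comparison group. An upward shift is likely; its size is unknown.

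This rests on two assumptions. First, the professionals who collect client sheets overlap with those who deliver RTM, which follows from the eligibility criteria read with the collection rule. Second, people tend to answer more favourably when an interested party will see the answer.

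A reader might go further and conclude that the acceptability result is known to be inflated or is worthless. The Protocol does not support that: it gives no size for the shift, and the case statistics offer a less exposed line of evidence. This is a cheap improvement to a stated procedure. It corrects no contradiction or miscalculation, and it has no bearing on the Study 1 outcomes.

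**What to change.** Amend the data collection text in Section 5 (Study 2) and Section 6 (Data access):

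1. **Clients.** The client seals the satisfaction sheet in an envelope or drops it in a closed box that only the coordinator opens, and is told beforehand that no professional delivering treatment will see the answers.
2. **Professionals.** Each partner's coordinator receives, opens and enters the sheets of the other partner's professionals, and runs the other partner's focus group. Anonymisation before input to EUSurvey stays as Section 6, Study 2 has it, and access remains with the two coordinators.
3. **Reporting.** State any remaining courtesy bias as a limitation of the acceptability conclusion, and present the case statistics beside the ratings.

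The cost is envelopes or boxes, some logistics between the two sites and a short protocol amendment; no extra staff are needed. The fix reduces the problem but does not remove it. Both coordinators belong to implementing partners, so an organisational interest remains, and the coordinator still sees the client sheets.

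Direct coded entry by respondents on EUSurvey may look simpler, but it would bypass the rule that coordinators anonymise and aggregate before input. With place of work recorded in groups of 10, it could also move a re-identification risk onto the transfer platform. It is therefore not proposed.
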